14.3. Data handling and record keeping

The dataset will be used for the sole purpose of the TARGIT-B trial.

Only authorised individuals will have access to person identifiable data. The TARGIT Operations

Group makes a commitment to maintaining the confidentiality, safety, security and integrity of all

confidential and sensitive data, which is held under its guardianship.

Staff in the TARGIT Operations Group are obliged to fully comply with The Data Protection Act

1998, together with all relevant rules of the sponsor organisation (UCL, London).

Where patients are willing, at randomisation they can provide mobile phone numbers and email

addresses for long term follow up. All such electronic identifiable data is kept in a dedicated database

in a secure data vault, separate from anonymised data. The study database is held on a dedicated

database server. The Surgical & Interventional Trials Unit network, a subnet of the UCL network, is

protected by a firewall and is behind UCL's institutional firewall. Both firewalls are managed by

UCL's network group. Access to server and the Surgical & Interventional Trials Unit network is

password & access right controlled. Access to identifiable data is controlled by staff roles and

passwords.

Data transfer and storage

The data will be sent to the TARGIT Operations Group via one of three routes: (1) a secure online

file transfer system, (2) to a fax machine located in a locked room within a locked building, (3)

through the post. Note that the TARGIT Operations Group can only accept responsibility for the data

after it has arrived in their custody.

The data will be retained by the TARGIT Operations Group until 20 years after the final publication

from the trial.

TARGIT B Protocol IRAS No: 77045

Version 6.0, Dated 10/09/2018

Page 33 of 46

Specific details regarding data storage and destruction are covered in a separate document available from the TARGIT Operations Group on request.

15. Statistical considerations

The Trial Statistician has primary responsibility for the statistical aspects of the trial.

15.1. Sample size calculation

In the Oxford overview of December 2005 ²⁵ of 10 BCS trials that started in 1995, patients who were node positive had a local recurrence rate of 11%. In the more recent EORTC trial, the boost arm ^{2 26-28} had a local recurrence rate for patients <41 at 5 yrs of 9.5% and at 10 years of 13.5% and for patients 41-50, 8.7% at 10 years. Although the overall 10-year local recurrence rate was 6.2%, the recurrences were "concentrated" in the younger patients. Furthermore, the trial population was at low risk of recurrence- most tumours were <2cm and 91.9% were node negative. On the other hand, the TARGIT-B trial will focus on patients aged 45 or less, or with adverse features. Considering that local recurrence rates are reducing substantially with modern systemic therapy, we have estimated that the local recurrence rate in the conventional arm will be 5.64%.

[figure not shown]
In the long term results of our pilot series of 299 patients which received the proposed experimental treatment had even higher risk tumours (29% node positive vs. 20% node positive in the overview), but had the actuarial 5 year local recurrence rate of 1.73% ¹¹ ¹², which was about half of the expected recurrence rate in this unselected group of patients. In women <50, this study had a local recurrence of 2.1% (SE 1.5). Thus we shall take the conservative estimate of 2.9% (2.1+0.5xSE=2.9%) as the expected recurrence in the experimental arm.

Therefore, the study will be powered to detect a difference between 5.64% and 2.9% (OR=0.5, exponential hazard rate of 0.80) and will need 1707 patients. (Two sided RCT with alpha=0.05 and power=80%. Assuming an attrition of 5%, we shall aim towards an accrual goal of 1796 patients, i.e., a sample size of 898 in each group.

The study is powered for a 5 year- recurrence rate. The hazard of local recurrence peaks between 2-3 years hence we have chosen the 3-year time point for the interim analysis. An interim analysis will be performed at a median follow up of 3 years, or after 41 events, whichever is earlier. At this point may revise the sample size by considering both efficacy and futility analysis. The DMC will of course regularly review the data for both safety and efficacy as per MRC guidelines.

Using Lan-DeMets Alpha spending function with O'Brien-Fleming Boundary to reject null hypothesis.

Cumulative Patient Accrual	Alpha Spent			
~1000 (41 events)	0.003			
1796	0.035			

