Simple cost diaries will be sent to each patient after randomisation, these instruments will be sent out by the TARGIT Trials Office and returned to the TARGIT Trials Office. Cost data will be collected only during the first three years of the study. Please see questionnaire schedule for data collection points. Diaries will be sent out at the beginning of the appropriate time window.

Questionnaire Schedule:

	Baseline (before surgery)		6	12	18	24			36	48	60
EQ5D &	√ V		V	V	√	V			$\sqrt{}$	V	√
FACTB+4											
		0-3	3-6	6-12	12-18	18-24	24-30	30-36			
Cost diary		1	1	V	$\sqrt{}$	1	V	$\sqrt{}$			

9. Subject selection

The trial will accrue from the centres already participating in the TARGIT-A trial, although many more centres are keen to participate. The TARGIT-A trial accrued patients from around the world (21% from UK, 56% from Europe, 13% from Australia and 10% from North America) but both the trials have been conceptualized, designed, initiated, administered and published from the UK. With the trial inclusion criteria being selective for high risk women, we conservatively estimate the accrual rate to be 5 patients per week (250 per annum) after one year.

Inclusion criteria

Patients diagnosed with breast cancer and suitable for conserving surgery and whole breast radiotherapy, with a histological confirmation of carcinoma can be included in the study once a written informed consent is obtained. All patients should be available for regular follow-up (according to local policies) for at least ten years.

At least one of these criteria must be satisfied:

- 1. Less than 46 years of age
- 2. More than 45 years of age and with one or more of the following poor prognostic factors:
 - a) Grade 3
 - b) ER and/or PgR negative
 - c) lobular carcinoma
 - d) extensive intraductal component (EIC)
 - e) lymphovascular invasion
 - f) axillary nodal involvement
 - g) more than one tumour in the breast but still suitable for breast conserving surgery through a single specimen
 - h) any factor or a combination of factors that puts the patient at a higher risk of local recurrence as per the current local guidelines: e.g., those who need a tumour bed boost or those *not* suitable for TARGIT-Alone as standard treatment.
- 3. Those patients with large tumours which have responded to neo-adjuvant chemo- or hormone therapy that is given in an attempt to shrink the tumour, and are now suitable for breast conserving surgery as a result.

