Randomisation schedules will be prepared using a bespoke SAS program, blocked and stratified by centre and stratum, with equal allocation between treatment arms, by the Trials Operations Office. The schedules will be accessible by authorised staff only. Requests for randomisation can be made by either fax (receipt of a completed inclusion/exclusion criteria checklist) or telephone. A trained member of staff will confirm eligibility and perform the randomisation, according to the Standard Operating Procedure. The turnaround time for faxed randomisations is next working day, for telephone randomisations immediate provided the call is made between 09.00 and 17.30 UK time.

The randomisation codes will be included in the data sent to the Trial Statistician for analysis.

13. Blinding & other measures taken to avoid bias

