15.2. Statistical analysis

Planned Statistical Analysis: The primary endpoint is the incidence of local recurrence. All comparison will be done on an "intent to treat" basis where all randomised patients will be included in the statistical analysis. Between-treatment group comparisons of proportion of local recurrence will be compared using simple Chi-squared test. Kaplan-Meier curves and log-rank test will be used to compare the time to local recurrence in the two treatment arms. Proportional Hazard regression models will control for possible confounding variables when comparing local recurrence in the treatment groups. We will report 95% confidence intervals for all reported proportions and hazard ratios.

Interim Analysis: Interim analyses will be carried out when 41 events occur or at a median follow up of 3 years, whichever is earlier. We have chosen 3 years because it will include the peak of hazard of local recurrence. This analysis will include the assessment for the need to change the sample size, as well as futility analysis about the continuation of the trial.

In addition, analysis of data will be carried out regularly by the DMC as per MRC guidelines.

Handling of loss to follow up or missing data: In order to carry out an Intent To Treat (ITT) analysis and avoid potential bias resulting from missing data, multiple imputation methods will be used after the missingness mechanisms are established. A full report of the patterns of missing data will be reported based on the recent CONSORT guidelines²⁹. Sensitivity analysis will be carried out and reported.

Planned subgroup analyses: This will include immediate vs. delayed boost (as a second procedure), pre- vs post- menopausal chemotherapy vs. no chemotherapy, neo-adjuvant vs. other, ER, PgR, HER2 status, Oncotype DX score. Further factors will be decided before unblinding of the data.

16. Compliance and withdrawal

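### Section 15.1 sizes the trial at two-sided alpha 0.05, but its alpha-spending table ends at 0.035 (0.038 if the rows are increments)

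*Protocol*

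**What the plan says.** Protocol section 15.1 powers the trial to detect a "difference between 5.64% and 2.9% (OR=0.5, exponential hazard rate of 0.80) and will need 1707 patients", under the specification "Two sided RCT with alpha=0.05 and power=80" per cent. It then adds attrition: "Assuming an attrition of 5%, we shall aim towards an accrual goal of 1796 patients, i.e., a sample size of 898 in each group".

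The same section describes an interim analysis at 41 events or a median follow-up of 3 years, whichever comes first. It closes with a short table introduced by "Using Lan-DeMets Alpha spending function with" an O'Brien-Fleming boundary. The first row (about 1000 patients, 41 events) has 0.003 of alpha spent. The last row (1796 patients, the accrual goal) has 0.035. The protocol does not say whether the column is cumulative, which form of the spending function was used, or why the last entry is not 0.05.

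Section 12 specifies randomisation "with equal allocation between treatment arms". Section 15.2 states that the "proportion of local recurrence will be compared using simple Chi-squared test".

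**The concern.** A spending function with total alpha 0.05 has, by construction, spent 0.05 when information is complete. The last row of the table is full accrual and reads 0.035. The sample size was worked at 0.05, so one section gives the final analysis two different significance levels.

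Two things are at stake. If the table governs, the trial has less power than the protocol states. And if the final p-value falls between the two levels, the superiority claim depends on which sentence is followed, a choice that should not be open once the data have been seen.

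**Working it through.** **Inputs (sections 12, 15.1 and 15.2).** p1 = 0.0564, p2 = 0.029, mean 0.0427; equal allocation; two-sided alpha 0.05; power 80%; chi-squared comparison of proportions; 1707 evaluable, 1796 accrued; interim at 41 events; alpha spent 0.003, then 0.035.

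**1. Reproduce the stated sample size.**
n per arm = [z(1-alpha/2) x sqrt(2 x 0.0427 x 0.9573) + z(0.80) x sqrt(0.0564 x 0.9436 + 0.029 x 0.971)]^2 / (0.0564 - 0.029)^2
= [1.960 x 0.2859 + 0.8416 x 0.2853]^2 / 0.0274^2 = 853.5, so 1707 in total.
Attrition: 1707 / 0.95 = 1796.8, against 1796 stated, a one-patient rounding. Both figures reproduce, so the sample size was worked at a full 0.05.

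**2. What the last row could mean.** Levels below come from bivariate normal integration over the two looks, with 0.003 spent at the interim.
- Cumulative: total alpha is 0.035 and the final nominal level about 0.034.
- Increments: total alpha is 0.003 + 0.035 = 0.038 and the final nominal level about 0.037.
- Final nominal level: 0.035 at the last test, with overall type I error about 0.036.

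A two-look design with total alpha 0.05 that spends 0.003 at the interim has a final nominal level of about 0.049. With the interim spend recomputed as in step 4, it is 0.048-0.049. None of the three readings of 0.035 gives a 0.05 design.

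**3. Power for 5.64% against 2.9%.**

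| Final analysis | 1707 evaluable | all 1796 |
|---|---|---|
| Single test at 0.05 | 80.0% | 82.0% |
| Two looks, 0.003 then total 0.05 | 80.0% | 82.0% |
| Single test at 0.035 | 75.6% | 77.8% |
| Two looks, total 0.035 | 75.5% | 77.7% |
| Two looks, total 0.038 | 76.6% | 78.7% |

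Putting 0.035 (z = 2.108) into the formula of step 1 gives 946.4 per arm. Rounded up, that is 947 per arm or 1894 evaluable, and 1894 / 0.95 = 1994 accrued.

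**4. Row 1.** Expected events over five years are 1707 x 0.0427 = 72.9 or 1796 x 0.0427 = 76.7, so 41 events is an information fraction t of 0.562 or 0.535. By patients, 1000/1796 = 0.557. With alpha/2 spent in each tail, the O'Brien-Fleming-type function is 4[1 - Phi(z(1-alpha/4)/sqrt t)].
- Total 0.05 (z = 2.241): 0.0056 at t = 0.562 and 0.0043 at t = 0.535. The value 0.003 belongs to t = 0.50.
- Total 0.035 (z = 2.376): 0.0031 at t = 0.562 and 0.0029 at t = 0.557, both rounding to 0.003. At t = 0.535 it is 0.0023.

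The single two-sided formula, 2[1 - Phi(z(1-alpha/2)/sqrt t)], gives 0.0074-0.0090 for a total of 0.05 and 0.0039-0.0049 for a total of 0.035. Row 1 therefore disagrees with a total of 0.05 under either form. It agrees with a total of 0.035 spent per tail at 41 of 73 events.

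**The case against.** The best defence is that the sample size is right. Section 15.1 states alpha 0.05, and at that level 1707 and 80% reproduce exactly. The table may be only a set of planning values, since a Lan-DeMets boundary is meant to be recomputed from the information actually observed. The discrepancy is also conservative: a final level of 0.035 does not inflate type I error. And section 15.2 includes all randomised patients, with multiple imputation for missing data. If all 1796 contribute, the loss against 80% is only about 1 to 2 points.

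Most of this stands and limits the size of the point. It does not remove the contradiction. Recomputing a boundary adapts the timing of the spend, but the total has to be fixed beforehand, and the protocol prints two totals. Section 17.1, which says there are no formal stopping rules, does not settle which one applies.

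Sections 15.1 and 15.2 also have the data monitoring committee review the data regularly, including for efficacy. Alpha reserved for those reviews could explain the missing 0.012 to 0.015, but the protocol does not say so.

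A reader might infer more than the document supports:
- That row 1 is wrong in itself. It is inconsistent only with a total of 0.05.
- That a middle look was lost from the table, because 0.003 + 0.012 + 0.035 = 0.05. The value 0.012 appears nowhere.
- That 41 events cannot coincide with about 1000 patients. Showing this needs an assumed hazard shape and accrual pattern. Section 15.1 says the hazard peaks at 2-3 years, and section 9 gives its rate of 250 a year only after the first year. Moreover, 41 / 0.0427 = 960, so the row is coherent as patients with a full five years at risk.

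**Conclusion.** The contradiction is real and lies within section 15.1: the sample size uses two-sided alpha 0.05, while the spending table ends at 0.035, or totals 0.038. It is a conflict between two statements, not an error in the sample-size calculation.

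Its size depends on the table's level being the one applied at the final analysis. In that case power is about 75-77% with 1707 evaluable patients and about 78-79% with all 1796, and a final p between 0.035 and about 0.048 has no agreed interpretation. If 0.05 is the total, the stated power holds. Calling the design a 76% design without that condition would go too far.

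The power figures assume the protocol's own event rates and its chi-squared comparison. The row 1 figures assume that information is measured against the 73-77 events expected over five years, a number that the protocol does not state. The fit of 0.003 to a total of 0.035 suggests that the table may have been built for that total, but does not prove it.

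**What to change.** State one total two-sided alpha in section 15.1, say whether the column is cumulative, and name the form of the spending function. Then do one of the following.

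- **Total 0.05.** End the table at cumulative 0.05 and recompute row 1 from the information fraction at the interim. With alpha/2 spent per tail, that is about 0.0043-0.0056 at 41 of an expected 73-77 events, with a final nominal level of about 0.048-0.049. Power stays at about 80% with 1707. The cost is wording only, with no extra patients.
- **Total 0.035.** Keep the table, state 0.035 as the total, and restate power as about 76% at 1707 evaluable. Keeping 80% instead would need 1894 evaluable patients, or 1994 with 5% attrition.

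Neither option requires an event-driven final analysis, which the protocol does not plan. If alpha is being held back for data monitoring committee reviews of efficacy, say so and give the amount. The choice should be made before comparative data are seen.

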15.2. Statistical analysis

Planned Statistical Analysis: The primary endpoint is the incidence of local recurrence. All comparison will be done on an "intent to treat" basis where all randomised patients will be included in the statistical analysis. Between-treatment group comparisons of proportion of local recurrence will be compared using simple Chi-squared test. Kaplan-Meier curves and log-rank test will be used to compare the time to local recurrence in the two treatment arms. Proportional Hazard regression models will control for possible confounding variables when comparing local recurrence in the treatment groups. We will report 95% confidence intervals for all reported proportions and hazard ratios.

Interim Analysis: Interim analyses will be carried out when 41 events occur or at a median follow up of 3 years, whichever is earlier. We have chosen 3 years because it will include the peak of hazard of local recurrence. This analysis will include the assessment for the need to change the sample size, as well as futility analysis about the continuation of the trial.

In addition, analysis of data will be carried out regularly by the DMC as per MRC guidelines.

Handling of loss to follow up or missing data: In order to carry out an Intent To Treat (ITT) analysis and avoid potential bias resulting from missing data, multiple imputation methods will be used after the missingness mechanisms are established. A full report of the patterns of missing data will be reported based on the recent CONSORT guidelines²⁹. Sensitivity analysis will be carried out and reported.

Planned subgroup analyses: This will include immediate vs. delayed boost (as a second procedure), pre- vs post- menopausal chemotherapy vs. no chemotherapy, neo-adjuvant vs. other, ER, PgR, HER2 status, Oncotype DX score. Further factors will be decided before unblinding of the data.

16. Compliance and withdrawal

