and other cancers), local toxicity/morbidity, cost-effectiveness and quality of life.

Separate sub-protocols, not included in this protocol, will address other endpoints, including cosmetic

outcome, cardiopulmonary toxicity, patient satisfaction and patient preference. These sub-protocols

will be subject to their own sponsorship and regulatory reviews.

TARGIT B Protocol IRAS No: 77045 Version 6.0, Dated 10/09/2018 8. Study design

Core Protocol: This pragmatic, parallel group, superiority randomised trial is designed to directly

compare the outcome, primarily in terms of local control, of two approaches of adjuvant radiotherapy.

Patients selected for breast-conserving surgery who are considered to have a high risk of local

recurrence are eligible to participate in the trial once they have received information and given their

consent.

Individual centres may choose to recruit only a subset of patients eligible as per the entry and

management criteria given in the protocol; for example some centres may decide not to enter patients

who require a second procedure solely to give the TARGIT-boost. These policies are to be

documented in advance and all trial patients treated according to this pre-declared policy. The study

will be analysed under an 'intention to treat policy' (ITT) with stratified analyses performed.

This trial allows entry of patients who are suitable, (or have been rendered suitable by neoadjuvant

systemic therapy) to be treated by breast conserving therapy and who are expected to have a high risk

of local recurrence, (young age, grade III histology, lymphovascular invasion, grossly involved

axillary nodes, etc.), or risk of recurrence in other quadrants of the breast such as extensive intraduct

component (EIC) or lobular carcinoma. Preferably, tumours should not be more than 4 cm in size, as

the largest applicator size is 5cm. Patient consent is sought and randomisation is carried out prior to

the surgical removal of the tumour. After wide local excision of the tumour, a tumour bed boost is

delivered using the Intrabeam system as described previously in the patients who are randomised to

TARGIT Boost. Those randomised to EBRT boost will have this boost delivered by conventional

External Beam Radiation Therapy (EBRT).

Most patients who require treatment for a metachronous breast cancer are excluded from entry to

trials of local treatment. Although there are good reasons for this, later development of recurrence

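### The primary comparison of local recurrence has no time point, is made by two unranked tests, and is unstratified despite stratified randomisation

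*Protocol*

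**What the plan says.** Section 15.1 fixes the horizon of the design: "The study is powered for a 5 year- recurrence rate". The rates are 5.64% in the conventional arm and 2.9% in the experimental arm, giving 1707 patients, raised to 1796 for 5% attrition.

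Section 15.2 does not carry that horizon forward:

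- Endpoint: "The primary endpoint is the incidence of local recurrence".
- Analysis set: intention to treat, "where all randomised patients will be included in the statistical analysis".
- First test: "Between-treatment group comparisons of proportion of local recurrence will be compared using simple Chi-squared test".
- Second test, on the same endpoint: "Kaplan-Meier curves and log-rank test will be used to compare the time to local recurrence in the two treatment arms".
- Model: "Proportional Hazard regression models will control for possible confounding variables when comparing local recurrence in the treatment groups". The covariates are not named.

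On stratification, section 12 says the randomisation schedules are "blocked and stratified by centre and stratum, with equal allocation between treatment arms", and section 8 defines five hormone-receptor strata. Section 8 also commits to an intention-to-treat analysis ("ITT) with stratified analyses performed") without naming a factor. Section 15.2 names no stratification factor and calls its chi-squared test simple.

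**The concern.** Patients will enter over about seven years and be followed for up to ten years or more, so at any data cut their observation times differ widely. A crude proportion counts a patient seen for six months in the same way as one seen for ten years. It estimates a 5-year rate only if it is restricted to patients with known 5-year status, and section 15.2 makes no such restriction.

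Three things are at stake.

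1. The quantity compared depends on the calendar date of the analysis.
2. Two tests bear on one endpoint and can disagree, with no rule for which one decides.
3. A crude proportion is exposed to differential loss in a way the log-rank is not. Allocation is open (section 13.1), follow-up is long (section 14.1), and data after withdrawal of consent are not used (section 16.2).

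These are methods the protocol states, so they are more than detail left to a later analysis plan.

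**Working it through.** **Inputs.** 5.64% and 2.9% at 5 years, two-sided 0.05, 80% power, 1707 then 1796 patients (section 15.1); 250 patients a year (section 9). Assumed: constant hazards, uniform accrual at that rate, and the loss rates shown below.

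**1. The plan's own sample size.** Uncorrected two-proportion formula with mean proportion p = 0.0427:

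n = [1.96·√(2p(1−p)) + 0.8416·√(0.0564·0.9436 + 0.029·0.971)]² / 0.0274² = 853.5 per arm.

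Twice this is 1707, as stated, and 1707/0.95 = 1796.8 (stated 1796). The sample size was therefore built on a chi-squared comparison of two 5-year proportions.

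**2. Implied hazards.** Control: −ln(1−0.0564)/5 = 0.01161 a year. Experimental: −ln(1−0.029)/5 = 0.00589 a year. Hazard ratio 0.507.

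**3. What the crude proportion estimates.** Accrual lasts a = 1796/250 = 7.18 years. At f years after the last entry the expected crude proportion is

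1 − [exp(−λf) − exp(−λ(f+a))]/(λa).

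For control at f = 0: 1 − (1 − 0.91997)/0.08341 = 4.1%.

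| Cut-off | Control | Experimental | Events |
|---|---|---|---|
| End of accrual (7.2 y) | 4.1% | 2.1% | 55 |
| 8.4 y | 5.4% | 2.8% | 73 |
| Last patient at 5 y (12.2 y) | 9.5% | 4.9% | 129 |
| Design value | 5.64% | 2.9% | – |

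Section 15.1 says the hazard peaks at 2 to 3 years, so a constant hazard overstates the last cut-off. Its own figures for patients under 41 (9.5% at 5 years, 13.5% at 10) give a ratio of later to earlier hazard of [ln 0.905 − ln 0.865]/[−ln 0.905] = 0.0452/0.0998 = 0.45. Applying that ratio after year 5 lowers the control figure from 9.5% to 7.4%.

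**4. Behaviour of the two tests.** Simulated trials with 898 per arm and exponential times. For type I error both arms have the control hazard. No imputation is applied.

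| Yearly loss, one arm vs the other (assumed) | Chi-squared, 8.4 y | Chi-squared, 12.2 y | Log-rank |
|---|---|---|---|
| 1% vs 1% | 4.5–4.8% | 4.5–4.8% | 4.4–4.8% |
| 1% vs 2% | about 5–6% | about 5–6% | about 5% |
| 1% vs 3% | 5.6% | 8.1% | about 5% |
| 1% vs 5% | 8.4% | 18.8% | 4.7–4.9% |

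In the last scenario at least one of the two tests is significant in 10.0% (8.4 y) and 21.2% (12.2 y) of null trials. With the declining hazard of step 3, its chi-squared figure at 12.2 years falls to about 12%.

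Under the design alternative with equal loss and about 73 events, power is about 80% for both tests (80.4% chi-squared, 80.3% log-rank).

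**5. Events needed if the log-rank is primary.** Schoenfeld: 4(1.96+0.8416)²/(ln 0.507)² = 68.02, so 69. Freedman: (1.96+0.8416)²·(1.507/0.493)² = 73.3, so 74. With 898 per arm each followed for 5 years, 898·(0.0564+0.029) = 77 events are expected; with 853.5 per arm, 73.

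**The case against.** The strongest reply is that the chi-squared is the test the sample size was calculated for (step 1), so test and design match. On complete 5-year status it would test exactly the powered quantity. That stands: what is missing is the horizon and the cut-off, and a reader who concluded that the chi-squared cannot test the 5-year rate would go too far.

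Four other strong readings are tempting and are not supported.

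- **Staggered entry biases the test.** It does not when entry and loss are alike in both arms. Step 4 shows nominal type I error and no loss of power.
- **The plan ignores unequal follow-up and the strata.** Section 15.2 also plans Kaplan-Meier curves, a log-rank test, Cox models, multiple imputation and sensitivity analyses. Section 8 intends balanced follow-up and promises stratified analyses. None of this supplies a time point, ranks the tests or names a factor. The fair statement is that sections 8 and 15.2 do not agree on stratification. Nor does the text call the two tests co-equal; it simply leaves them unranked.
- **The trial will have an inflated type I error.** This depends on differential loss. Loss of 1% against 5% a year means about 5% against 22% lost by 5 years, while section 15.1 plans for 5% attrition overall. Mild imbalance leaves the chi-squared close to 5%, and the planned imputation is not modelled here.
- **The final analysis happens when accrual ends, with about 55 events and power near 68%.** The 1796 in the alpha table is a row label under cumulative accrual. No text makes it the timing rule.

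It is also fair that a 5-year proportion on complete follow-up would be an acceptable alternative. The log-rank is preferred because it uses partial follow-up, tolerates unequal loss better here and costs no power.

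**Conclusion.** The concern holds in this limited form. As written, section 15.2 does not fix the confirmatory analysis: it gives a crude proportion with no time point and two unranked tests, and its lack of stratification does not match sections 8 and 12. The control proportion under comparison ranges from about 4.1% to 9.5% with the cut-off (constant hazard, 250 patients a year), or to about 7.4% at the late cut-off if the hazard declines as section 15.1 suggests. With equal loss there is no bias and no difference in power. With unequal loss the chi-squared type I error runs from about 5 to 6% (1% against 2% a year) to about 8% at 8.4 years and 18 to 19% at 12.2 years (1% against 5% a year). These loss rates are assumptions, not forecasts, and the figures are before imputation. The log-rank stays near 5% throughout.

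**What to change.** In section 15.2:

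- Name a log-rank test stratified by the hormone-receptor strata of section 8 as the single primary test. Report a Cox hazard ratio with the same stratification and the 5-year Kaplan-Meier difference, each with its 95% confidence interval.
- Label the chi-squared test supportive, or restrict it to patients with known 5-year status.
- State the final cut-off, either as an event count or as 5 years of follow-up. About 69 to 74 events give 80% power at a hazard ratio of 0.507 and two-sided 0.05, before any adjustment for the interim look.
- Reconcile sections 8 and 15.2: name the stratification factors and say how centre is handled. Crossing every centre with every receptor stratum would give too many cells for some 70 events, so a coarser grouping such as region is more workable.

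The sample size need not change and no extra data are needed. The cost is protocol and SAP wording, and it should be settled before any unblinded comparison.
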